## **COVID-19 Testing Information and Procedures**

COVID-19 testing strategies and implementation of testing procedures occur outside of this study's scope, therefore is not determined by the research team. Screening and symptomatic testing is being offered (but not mandated) to Yakima School District students through the Yakima School District static testing site. The possibility for the Yakima School District to implement weekly testing in schools for all students may occur at a later time in the study period. The test currently being utilized is the BD Veritor System for Rapid Detection of SARS-CoV-2. SARS-CoV-2 testing will be offered to students on a weekly basis. The BD Veritor rapid antigen test conducted by the Yakima School District is CLIA approved by the WA DOH.

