## 2. Study Schema and objectives

[figure not shown]
Purpose:	To determine the effectiveness of risk communication for parents and students on students' attendance to school, COVID-19 testing and vaccine uptake
Design:	A clustered randomized controlled trial of risk communication intervention
Central Hypotheses:	Our central hypotheses are that students and parents who view the risk communications will be more likely to have less school absence, increased covid-19 testing and vaccine uptake.
Primary Objectives:	

• To determine if implementing three COVID-19 education comic books for children and two COVID-19 education videos for parents will lower school absenteeism, increase COVID-19 testing, and vaccine uptake in children.

Secondary Objectives:	

• To determine if implementing three COVID-19 education comics books for children and two COVID-19 education videos for parents will increase physical activity, improve sleep, increase emotional regulation in children.

• To determine if implementing three COVID-19 education comics books for children and two COVID-19 education videos for parents will increase physical activity, improve sleep, decrease depression and anxiety in parents

Population:	Children ages 5-13 enrolled in kindergarten to 5 th grade in Yakima School District
Study Size:	14 schools randomized; 7 to intervention and 7 to comparison arms with 450 children in each arm; a total of 900 children from 14 schools.
Primary Outcome Measurements:	

A. Attendance captured through the school district

B. COVID-19 testing data available through the school district testing program and self-reported survey

C. COVID-19 vaccine data available through self-reported survey

Study Duration:	2 years including enrollment period, 2 months to deliver the intervention, 5 months for post 1 survey, 7 months weeks for post 2 survey.

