## 5. Population and Data Source

Participants enrolled in the ROSSEY Study: 900 children and parents from the Yakima School District. Any randomized participants subsequently found to be ineligible will be removed. The data sources for the primary analyses are the attendance records and positive COVID testing results received from the school administration and the survey data as entered in REDCap. COVID Vaccination status data is obtained through the parent and child surveys that are completed in REDCap.

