## 7. Outcome Definitions

### a. Primary Outcomes

The three co-primary outcomes for the trial are school absenteeism, COVID-19 testing, and COVID-19 vaccine uptake. Absenteeism are the student's school attendance data for 2022-2023 school year, COVID-19 data are captured through school testing and self-reported survey, and COVID-19 vaccine uptake data are captured through self-reported survey. All children and parent data after randomization will be included in the intention to treat analysis.

**Absenteeism:** total number of school days missed by each individual student participant, both for the entire school year and month-by-month, as captured and shared with us by school district administrative data systems. Absenteeism will also be measured by school days missed and will be a count variable.

**COVID-19 testing:** Health reports from the school are provided for the 2021-2022 and 2022-2023 school year that list positive covid test results of study participants with the date of testing and the school of attendance. Positive COVID test results will be a binary yes/no variable.

**COVID-19 vaccine uptake:** Parents are asked at enrollment to report their vaccination status and their child's vaccination status. At post survey 1 and post survey 2 the parent is asked to report if they or their child have received any COVID-19 vaccine or booster since enrollment. Vaccination status will be a binary yes/no variable.

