### *Inferential Analyses:*

To determine if absenteeism differs between participants given COVID-19 educational material and the participants in the control group, we will conduct a complete-case analysis to compare mean absences between the intervention and control groups using a two-sample t-test.

We hypothesis implementing three COVID-19 education comic books for children and two COVID-19 education videos for parents will lower child's absenteeism and COVID infection rates and increased vaccine uptake.

School days missed will be modelled by a mixed zero inflated negative binomial model, with school specific random effects to account for clustering. COVID positive testing results will be modelled by a mixed logistic regression model, with school specific random effects to account for clustering.

Vaccine uptake will also be analyzed by mixed logistic regression model.

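### The infection hypothesis is tested on district-recorded positives from voluntary testing that the intervention aims to raise, so a null result or an odds ratio above 1 says nothing about infection

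*SAP*

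**What the plan says.** The SAP's Inferential Analyses paragraph (section 12.c.ii) predicts that the materials "will lower child's absenteeism and COVID infection rates and increased vaccine uptake". The analysis that goes with the infection part is: "COVID positive testing results will be modelled by a mixed logistic regression model, with school specific random effects to account for clustering".

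Section 7.a builds the outcome from school health reports "that list positive covid test results of study participants with the date of testing and the school of attendance" and codes it simply: "Positive COVID test results will be a binary yes/no variable". Section 5 gives the same source: "attendance records and positive COVID testing results received from the school administration". Section 7.a also says that "COVID-19 data are captured through school testing and self-reported survey", but it defines no self-reported infection variable.

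On testing, the Protocol (COVID-19 Testing Information and Procedures) states: "Screening and symptomatic testing is being offered (but not mandated) to Yakima School District students through the Yakima School District static testing site". SAP section 2 gives the central hypothesis that "students and parents who view the risk communications will be more likely to have less school absence, increased covid-19 testing and vaccine uptake", and its primary objective also includes raising testing. The Risk Communication paragraph of the Protocol confirms that the materials promote testing.

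**The concern.** Under this coding, a child who was infected but never tested counts as a no, exactly like a child who was not infected. An infection enters the data only if the child is tested through the district while infected. The intervention is meant to change whether that happens.

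Two of the trial's own hypotheses therefore pull this one variable in opposite directions: more testing raises it and less infection lowers it. Nothing in either document adjusts for testing, uses positivity among tests performed, or plans a sensitivity analysis for a testing difference between arms. A campaign that succeeded in raising testing could be reported as having raised children's infections, or a real fall could be reported as no effect.

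**Working it through.** **The plan's own figure.** The documents give no power, infection rate or testing rate for this hypothesis. The nearest stated figure is 90% power for a 4-hour attendance difference (SAP section 4: SD 8.0, 7 schools per arm, 50 children per school, ICC 0.05). The design effect is 1 + 49 × 0.05 = 3.45, so the effective size is 350 / 3.45 = 101.4 per arm. A noncentral t with 14 − 2 = 12 degrees of freedom gives 90.4%, which reproduces the SAP; a normal approximation gives 94.5%. The same t method is used below.

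**What the model compares.** Ignoring false positives, P(recorded positive) = P(infected) × P(infection recorded). Let the recording ratio be P(recorded) in the intervention arm divided by that in control. A relative fall f in infection is fully hidden when the recording ratio is 1 / (1 − f):
- 20% fall: 1 / 0.8 = 1.25
- 30% fall: 1 / 0.7 = 1.43

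This step needs no assumed rates.

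**Inputs for the size.** From the SAP: 7 schools and 450 children per arm (450 / 7 ≈ 64.3 per school), ICC 0.05, two-sided 0.05. Assumed: 30% infected and 30% of control infections recorded, with ICC 0.01 as a second value. The design effect is 1 + 63.3 × 0.05 = 4.16, or 1.63 at ICC 0.01. The standard error is √[(p₀(1 − p₀) + p₁(1 − p₁)) × design effect / 450], and the noncentrality is (p₁ − p₀) / SE.

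Worked case, 30% v 45% recorded: p₀ = 0.30 × 0.30 = 0.090 and p₁ = 0.30 × 0.45 = 0.135. The odds ratio is (0.135 / 0.865) / (0.090 / 0.910) = 1.58. At ICC 0.05, SE = 0.0429 and the noncentrality is 1.05.

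**Equal infection (true odds ratio 1.00):**

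| Recorded, control v intervention | Positives | Odds ratio | Significant towards harm, ICC 0.05 | ICC 0.01 |
|---|---|---|---|---|
| 30% v 30% | 9.0% v 9.0% | 1.00 | 2.5% | 2.5% |
| 30% v 40% | 9.0% v 12.0% | 1.38 | 10% | 18% |
| 30% v 45% | 9.0% v 13.5% | 1.58 | 16% | 34% |
| 30% v 50% | 9.0% v 15.0% | 1.78 | 24% | 52% |

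With infection at 20% or 40% and 30% v 45% recorded, the odds ratio is 1.55 or 1.61.

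**Real falls in infection:**

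| Infection | Recorded | Odds ratio | Significant benefit, ICC 0.05 | ICC 0.01 |
|---|---|---|---|---|
| 30% v 15% | 30% v 30% | 0.48 | 23% | 49% |
| 30% v 15% | 30% v 50% | 0.82 | 6% | 9% |
| 30% v 24% | 30% v 30% | 0.78 | 6.5% | 10.7% |
| 30% v 24% | 30% v 45% | 1.22 | 0.9% | 0.4% |

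In the last row a true odds ratio of 0.74 appears as 1.22, on the wrong side of 1.

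**Check against the planned model.** The t test only approximates the mixed logistic model. Two independent sets of 600 simulated trials per setting used that model with 64 children per school and a school SD of 0.72 on the logit scale (ICC roughly 0.03 to 0.06). Rejection towards harm was 12% to 17% at 30% v 40% recorded and 32% to 33% at 30% v 50%. Total rejection with no difference was about 7% to 8%, so part of the excess over the table is small-cluster inflation.

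**The case against.** **Infection may not be a real objective.** Infection rates appear as a hypothesis only in this one SAP sentence. Sections 2 and 7.a list testing in the same position, so the word may be a drafting slip, and the deeper problem may be that the testing outcome is defined by positives. That is fair. But repairing the testing outcome would leave this sentence and its model in place, so the wording still has to change.

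**Both arms are encouraged to test.** Reminders and the $5 card (Protocol, Study Compensation) go to everyone and may narrow a difference. They remove the bias only if they make testing equal, and then the testing objective has failed.

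**Self-report is a second source.** No self-reported infection variable is defined, and the weekly check-in is described as asking whether the child was tested at the static site. A self-reported result would also depend on being tested.

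**A reader might infer that no result in either direction can be read.** The documents do not support that. If testing rises, the bias runs only upward, so a significant odds ratio below 1 would understate a fall. With equal infection and 30% v 45% recorded, a false significant benefit occurs about 0.2% of the time at ICC 0.05.

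**A reader might also expect much higher false-harm rates.** Those need less variation between schools than the SAP assumes. A school SD of 0.4 on the logit scale at 9% positives is an ICC of only about 0.4² × 0.09 × 0.91 = 0.013, against the SAP's 0.05.

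**Nor is a missed fall due to recording alone.** With equal 30% recording, power for halved infection is already only 23% to 49%.

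**Conclusion.** The concern holds in one direction. If the intervention raises testing, the planned model is biased upward as a test of infection: a null result or an odds ratio above 1 supports no conclusion about infection, and a real fall can be hidden. An odds ratio significantly below 1 would be conservative evidence of a fall, but only if testing is shown to be no lower in the intervention arm.

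The direction follows from the SAP's definitions. The size does not, because the documents give no infection or testing rates. Under the rates assumed above, the chance of a significant result towards harm with equal infection is 10% to 24% at the SAP's ICC and 18% to 52% at ICC 0.01. Those percentages illustrate the risk and do not predict the result.

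**What to change.** - In the Inferential Analyses paragraph, replace infection rates with district-recorded (detected) positive results, and predict no direction for them, since more testing raises them.
- Take this model out of the confirmatory primary tests. Section 10 does not say which tests the FDR control covers, so the SAP should state that this one is outside it.
- Section 12.c.i already plans counts of positives by arm. Show beside them the number of children tested, from district records if the data agreement supplies them, otherwise from the weekly check-in testing item.
- State in advance that a null result or an odds ratio above 1 supports no conclusion about infection, and that one below 1 is read only with the testing comparison.
- Parent-reported symptoms from the weekly check-in may be shown as exploratory only. They are subject to non-response, and reporting may differ by arm because only intervention parents receive the videos during follow-up.

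The cost is SAP wording and one table from data already planned for collection. The trial gives up a confirmatory claim about infection.

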## iii. Secondary outcomes

The secondary outcomes for the trial include measures from the PROMIS – Pediatric and Parent Proxy Instruments. The PROMIS instruments used are Children's PA, sleep, stress, depression, and anxiety; Parents' PA, sleep, stress, depression and anxiety. We will compare the scores for each of the items between the control and intervention arms at months 5 and 7. We will use a linear mixed effects regression models to determine whether between-arm differences were statistically significant.

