**After enrollment is complete, parents/guardians of study participants will take part in the following study procedures:**

**Figure 2. Outline of Study Procedures**

**Weekly Check-in Survey:** Parents of enrolled students will be asked to complete an online weekly 5-minute survey throughout the duration of the study that asks if their child is experiencing symptoms consistent with COVID-19 and has sought health care, if they have been absent from school in the past week, or if they have been exposed to someone with suspected COVID-19. Parents will also be asked if their child has been tested for SARS-CoV-2 at the Yakima School district static test site.

**Secondary Outcome Assessments:** Participants will be asked to participate in secondary outcome assessment surveys for the index child in each family collected either online, on paper, or by phone, based on their preferences. The index child will be selected based on the child with the most recent birthday from the time of enrollment if there is more than one child enrolled in a family. The goal is to conduct 900 secondary outcome assessments: 450 parents of children in the intervention group and 450 parents of children in the control group. Study surveys are available in both English and Spanish, as chosen by the participating parent or guardian.

Parents will be asked to complete surveys on topics such as their own and their child's perceived stress, sleep disturbance, physical activity, and emotional regulation (including both depressive and anxiety symptoms). Secondary outcome survey assessments will be offered to participants to be completed at the time of enrollment, halfway through the study (month 4), and at the end of the study (month 6). In order to better understand potential moderators and mediators of intervention effects, these surveys will also assess health literacy (at enrollment only), positive and negative outcomes expectations around testing and vaccines, and self-efficacy around testing, mask use, discussing COVID-19 with a healthcare provider and risk communication/information relevancy.

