### **XIV. DEFINITIONS**

**Acute Respiratory Illness (ARI):** We will use the CDC definition of ARI that includes disease that typically involves the airways within the nose and throat and may or may not include fever. ARI is generally defined by the presence of two or more symptoms such as fever, cough, runny nose or nasal congestion, or sore throat. ARI is more sensitive (broader) than influenza-like illness to describe illness consistent with influenza because fever/feverishness is not required.

**Exposure/Close contact:** Per CDC definition, a close contact is someone who was less than 6 feet away from infected person (laboratory-confirmed or a clinical diagnosis) for a cumulative total of 15 minutes or more over a 24-hour period (for example, *three individual 5-minute exposures for a total of 15 minutes*).

- **Exception:** In the **K-12 indoor classroom** setting or a structured outdoor setting where mask use can be observed (i.e., holding class outdoors with educator supervision), the close contact definition excludes students who were between 3 to 6 feet of an infected student (laboratory-confirmed or a clinical diagnosis) if both the infected student and the exposed student(s) correctly and consistently wore well-fitting masks the entire time.

**Laboratory Confirmed COVID-19 Infection:** an individual who tests positive for SARS-CoV-2 via an approved rapid antigen or PCR test.

**Absenteeism:** total number of school days missed by each individual student participant, both for the entire year and month-by-month, as captured and shared with us by school district administrative data systems.

**Emotion Regulation:** these can also be referred to as “internalizing symptoms”, or as depressive and anxiety symptoms.

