### b. Secondary Outcomes

Secondary outcomes for the trial include the following outcomes from the PROMIS – Pediatric and Parent Proxy Instruments. The PROMIS instruments used are Children's physical activity (PA), sleep, stress, depression, and anxiety. Parents' PA, sleep, stress, depression and anxiety. The final score is represented by the T-score, a standardized score with a mean of 50 and a standard deviation (SD) of 10.

The outcome measures will be collected at baseline, and months 5 and 7 surveys.

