#### i. Descriptive Analyses:

Positive COVID test results from the school district testing program will be summarized by counts by randomization group. Vaccine status and covid testing results will be summarized by counts and percentages by randomization group. Continuous variables by mean, standard

deviation(SD) and median (IQR) by randomization group. Secondary outcomes will be summarized and compared using Chi-squared tests

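### PROMIS T-scores are collected at baseline, but the SAP gives the baseline score no stated role in the between-arm comparison at months 5 and 7

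*SAP*

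**What the plan says.** SAP 7.b lists PROMIS measures of physical activity, sleep, stress, depression and anxiety for children and the same five for parents, ten scores in all. The final score is the T-score, "a standardized score with a mean of 50 and a standard deviation (SD) of 10". On timing it says: "The outcome measures will be collected at baseline, and months 5 and 7 surveys".

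SAP 12.c.iii gives the analysis in two sentences: "We will compare the scores for each of the items between the control and intervention arms at months 5 and 7", followed by "We will use a linear mixed effects regression models to determine whether between-arm differences were statistically significant". It lists no fixed effects, random effects, covariates or time structure. SAP 12.b tabulates baseline characteristics, but no SAP section brings the baseline PROMIS score into the between-arm comparison.

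Three neighbouring statements do not fit together:

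- SAP 12.c.iii refers to items, whereas SAP 7.b makes the T-score the final score.
- SAP 12.c.i says: "Secondary outcomes will be summarized and compared using Chi-squared tests". That does not suit a continuous T-score and differs from the mixed model.
- The protocol's outline of Aim 2 procedures puts the two follow-up assessments at months 4 and 6, not 5 and 7.

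On direction, the child objective in SAP 2 is to "increase physical activity, improve sleep, increase emotional regulation in children", and the parallel parent objective is to lower depression and anxiety. Protocol XIV says that emotion regulation can also be called internalizing symptoms, "or as depressive and anxiety symptoms". The protocol's description of the secondary outcome surveys uses the term in the same way.

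**The concern.** The baseline T-score is likely to be the best single predictor of the same score a few months later, and it is already in the database. The text as written leads an analyst to a follow-up-only model. Another analyst could add the baseline score, or use change scores, and claim equal compliance with the SAP. With ten scores at two time points, that choice should be closed before the data are analysed.

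Two things are at stake. The first is precision: with 7 schools per arm the detectable differences are wide, and an available covariate would narrow them. The second is exposure to chance: only 14 schools are allocated, so the arms may start apart on some scores, and part of such a gap would persist into the unadjusted follow-up difference.

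A smaller matter is which sign counts as benefit. If emotion regulation means depressive and anxiety symptoms, an objective to increase it points the opposite way to the parent objective. The SAP names no separate emotional regulation instrument and states no beneficial direction for any T-score.

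**Working it through.** **Inputs from the documents.** T-score SD 10 (SAP 7.b); 7 schools and 450 children per arm (SAP 2), with the same 450 per arm as the protocol's target for secondary outcome surveys, one index child per family. Average school size is 450/7 = 64.3.

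**Inputs assumed.** The documents give no ICC and no baseline to follow-up correlation r for any PROMIS score. I use ICC 0.01 to 0.05 (SAP 4 uses 0.05, but for attendance and vaccination) and r = 0.5 to 0.7. Equal school sizes are assumed and pair matching is ignored.

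**Check of the method on the SAP's own figure.** No power figure is given for PROMIS outcomes, so there is none to reproduce. For attendance (SAP 4: difference 4, SD 8, 50 students per school, ICC 0.05) the design effect is 1 + 49 × 0.05 = 3.45. The standard error is 8 × √(2 × 3.45/350) = 1.12. Power is 90.4% with a t distribution on 12 df (14 schools minus 2), which agrees with the stated 90%. The normal approximation gives 94.5%.

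**Step 1. Chance baseline difference between arms.** SD = 10 × √(ICC × 2/7 + (1 − ICC) × 2/450).

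- ICC 0.01: 10 × √(0.00286 + 0.00440) = 0.85 points; 95% range ±1.96 × 0.85 = ±1.7.
- ICC 0.05: 10 × √(0.01429 + 0.00422) = 1.36 points; 95% range ±1.96 × 1.36 = ±2.7.

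A gap of 2 points or more would occur in about 2% of allocations at ICC 0.01 and 14% at ICC 0.05, for each score. If r is 0.5 to 0.7 and the SD is stable, about 1.0 to 1.4 points of a 2-point gap would be expected to remain at follow-up (2 × r).

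**Step 2. Variance removed by adjustment.** The fraction remaining is 1 − r²: 0.75 at r = 0.5 and 0.51 at r = 0.7. So 25 to 49% is removed, at each level (school, child) where that correlation holds.

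**Step 3. Effect on the standard error of the arm difference.** The unadjusted standard error equals the SD in Step 1.

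If the correlation holds at both levels, the standard error is multiplied by √0.75 = 0.87 or √0.51 = 0.71, a fall of 13 to 29%.

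If it holds at child level only, just the second term shrinks:

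- ICC 0.05, r = 0.5: √((0.01429 + 0.75 × 0.00422)/0.01851) = 0.971, a fall of 3%.
- ICC 0.05, r = 0.7: √((0.01429 + 0.51 × 0.00422)/0.01851) = 0.942, a fall of 6%.
- ICC 0.01, r = 0.5: √((0.00286 + 0.75 × 0.00440)/0.00726) = 0.921, a fall of 8%.
- ICC 0.01, r = 0.7: √((0.00286 + 0.51 × 0.00440)/0.00726) = 0.838, a fall of 16%.

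The gain is small at ICC 0.05 because 0.01429/0.01851 = 77% of the variance lies between schools.

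**Step 4. Difference detectable with 80% power** (standard error × (2.179 + 0.873), t on 12 df, two-sided 0.05), in T-score points:

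| ICC | No baseline | r = 0.5, both levels | r = 0.7, both levels | r = 0.5, child only | r = 0.7, child only |
|---|---|---|---|---|---|
| 0.01 | 2.60 | 2.25 | 1.86 | 2.39 | 2.18 |
| 0.05 | 4.15 | 3.60 | 2.96 | 4.03 | 3.91 |

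**Sensitivity to sample size.** Protocol IV (Aim 3 criteria) reports about 290 intervention-arm parents with baseline surveys. If both arms had 290 (assumed), the Step 1 SDs would be 10 × √(0.00286 + 0.99 × 2/290) = 0.98 and 10 × √(0.01429 + 0.95 × 2/290) = 1.44.

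**The case against.** The strongest reply is that the SAP is silent on baseline and does not exclude it. A mixed model with three scheduled measurements could well include the baseline score. That is correct. A reader might infer that the SAP rules out baseline adjustment or fails to match its own objectives, but the text does not support this. An aim to raise activity or lower depression can be read as a between-arm contrast, and a follow-up difference estimates that contrast.

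A reader might also infer that the follow-up-only comparison is biased, or reports chance imbalance as an effect. It does not. It is unbiased over randomisations, and a model with a school effect carries chance school differences in its standard error. The 2% and 14% in Step 1 are tails of ordinary sampling variation and not additional false positives. Matching schools on English Language Learners and size would reduce imbalance further if those factors predict the scores.

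The precision gain is also less certain than the 13 to 29% alone suggests, because that range needs the same correlation between school means as between children. All of these points stand, and they limit the claim. They do not remove it: the better analysis uses data already collected, and the SAP does not commit to it.

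On direction, a reader might infer that the objective lets a rise in child symptoms count as success. The parallel parent objective shows that fewer symptoms are intended, the ordinary meaning of better regulation agrees, and no estimate or two-sided p-value changes. What remains is a conflict of wording.

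**Conclusion.** The point holds as a free improvement to an under-specified secondary analysis, not as an error that invalidates it. Baseline T-scores are collected and the planned comparison gives them no stated role. The cost is lost precision and exposure to chance imbalance in a single allocation of 14 schools. Under the assumed ranges (ICC 0.01 to 0.05, r 0.5 to 0.7, 450 per arm, no credit for matching), the standard error falls by between about 3% and 29%. Where in that range it lies depends mainly on whether baseline predicts follow-up between schools as well as between children, which the documents do not show. The emotional regulation wording is a secondary clarification.

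**What to change.** In SAP 12.c.iii:

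- Name the T-score as the endpoint in place of the reference to items.
- Specify a linear mixed model with a school random effect and the same measure's baseline T-score as a covariate. Alternatively, model baseline, month 5 and month 7 jointly, with arm means constrained equal at baseline. The joint model also keeps families whose baseline score is missing.
- Report the adjusted difference with its 95% confidence interval at each month.

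In the same edit, reconcile the Chi-squared statement in SAP 12.c.i with this model, and the follow-up months in the SAP with those in the protocol.

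As a minor clarification, bring the child objective in SAP 2 into line with the protocol's use of the term, for example by wording it as a decrease in depressive and anxiety symptoms. If a separate regulation measure is intended, name it. State the beneficial direction of each T-score.

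The cost is SAP wording only. No new data, visits or participants are needed.
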